#### 9.2.1 Study Period

The start of the study will commence at the first data abstraction of the first site. Charts for new eligible patients at each site will be included during the first 5 years of study.

Chart abstractions for each eligible patient will continue for a minimum of 2 years post Blincyto initiation. End of Study will be approximately 7 years after the first patient was enrolled, at which point the vast majority of still active patients will have their minimum of 2 years of follow-up.

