#### *Efficacy*

- Proportion of patients achieving CR (defined as < 5% bone marrow blasts, platelets > 100,000 cells per  $\mu\text{L}$ , and absolute neutrophil count > 1,000 cells per  $\mu\text{L}$ ) within 2 cycles of Blincyto treatment
- Proportion of patients achieving CR/CRh\*/Cri
- CR defined as < 5% bone marrow blasts, platelets > 100,000 cells per  $\mu\text{L}$ , and absolute neutrophil count > 1,000 cells per  $\mu\text{L}$ , or
  - CRh\* defined as  $\leq$  5% bone marrow blasts, platelets > 50,000 cells per  $\mu\text{L}$ , and absolute neutrophil count > 500 cells per  $\mu\text{L}$ , or
  - CRi defined as  $\leq$  5% bone marrow blasts and incomplete recovery of peripheral blood counts) within 2 cycles Blincyto treatment
- Proportion of patients receiving allogeneic HSCT. Defined for the subset of subjects who achieved CR.
- 1-year and 100-day mortality proportion after allogeneic HSCT. Defined for the subset of subjects who achieved CR.
- Relapse-free survival (RFS) time – defined as time from CR/CRh\*/CRi until relapse (proportion of blasts in bone marrow > 5% or blasts in peripheral blood after documented CR/CRh\*/CRi) or death. Defined for the subset of subjects who achieved CR.
- Disease free survival (DFS): defined as time from initiation of Blincyto (for minimal residual disease-positive [MRD+] patients at Blincyto initiation) until date of relapse or death
- Overall survival (OS) time – defined as time from initiation of Blincyto until death
- Proportion of patients with MRD among those who achieve CR/CRh\*/CRi within two cycles of Blincyto treatment - hematologic MRD detected by polymerase chain reaction (PCR) (or flow cytometry) at a level of  $1 \times 10^{-4}$  or higher.
- Efficacy outcomes (as described above) among patient subgroups defined by demographic and clinical factors (described in Section 9.7.2.3.4)

*Blinicyto utilisation & select health care resource use*

- Blincyto utilisation, for example:
  - Duration of Blincyto use (eg, number of completed cycles, total number of days of Blincyto administration)
  - Dosing pattern (eg, proportion of patients with step-up on day 8, number of cycles initiated, frequency of bag changes)
  - Proportion of patients with treatment changes (eg, interruption, discontinuation, dose reduction) as indicated by the SmPC after AEs (stratified by type of event)
- Select healthcare resource use, for example:

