**9.3.3 Covariate Assessment**

The patient and clinical characteristics listed below will be collected from medical records to provide descriptive information on the Blincyto-treated study population and as consideration for use as stratifying variables or for standardization:

- Patient age at date of treatment initiation (in years)
- Patient sex (male/female)
- Blincyto indication (eg, R/R ALL, MRD+ ALL, etc)
- ALL disease characteristics and treatment since disease diagnosis, during Blincyto treatment and through to end of study:
  - Date of ALL diagnosis
  - R/R status (yes/no for each)
  - MRD status in morphological CR
  - First relapse within 12 months of front-line treatment (yes/no)
  - Cytogenetics
  - Bone marrow blasts (%) at Blincyto initiation
  - Number of prior relapses
  - Prior ALL treatment regimens (number and type of treatment, including allogeneic HSCT and dates, and response to prior treatment regimens)
  - ALL treatment regimens after Blincyto completion

- Disease characteristics for indication other than ALL treatment since disease diagnosis, during Blincyto treatment (indication, date of diagnosis, prior treatment)
- Concomitant medications 7 days prior to Blincyto initiation, during Blincyto treatment and up to 30 days after treatment completion including, but not limited to other anti-cancer therapies (including radiotherapy) and other immunotherapies (both number and type of medications and treatment indication)
- Laboratory assessments 30 days prior to Blincyto initiation, during Blincyto treatment and up to 30 days after treatment completion (see details in [Appendix B](#)):
  - Biochemistry (including hepatic and renal function assessments)
  - Blood count (including Haemoglobin, Platelets, WBC, Neutrophils, Blasts)
  - Other labs (IgG, coagulation)
- Co-morbid conditions 1 year prior to Blincyto initiation and after Blincyto initiation including but not limited to active or history of central nervous system (CNS) pathology, hepatic impairment, renal impairment, active uncontrolled infections, human immunodeficiency virus (HIV) positivity, hepatitis B and C (both number of comorbidities and type of disease/condition)
- Date of Blincyto treatment initiation
- Graft-versus-host disease and associated prophylaxis for allogeneic HSCT after Blincyto treatment completion

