### **9.7.2 Planned Method of Analysis**

All analyses will be descriptive. Continuous variables will be summarised by mean, median, standard deviation, 25th percentile, 75th percentile, minimum and maximum. Categorical variables will be summarised by number and percentage. For categorical outcomes, 95% confidence intervals will also be presented where appropriate. For time-to-event endpoints, Kaplan-Meier (KM) curves and estimates (median, 1st and 3rd quartile) of the time-to-event endpoint with 95% confidence intervals will be calculated, if estimable. Six, 12- and 24-month survival proportions and 95% confidence intervals will also be estimated. Tables will be presented for the total patient population (ie, those who meet the eligibility criteria and have at least one dose of Blincyto) split by adult and paediatric patients and for disease subgroups with 15 or more patients, as well as for the subset of patients with LFR. Safety and efficacy data will also be tabulated by the patient subgroups described in Section [9.7.2.3.4](#).

The Medical Dictionary for Regulatory Activities (MedDRA) version 24.1 or later will be used to code all adverse events.

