| End of IP Administration (Blinatumomab)                           |          | X   |  |
| Antibody  |          | X   |  |
| Product Complaints  |          | X   |  |
| Other Safety Findings   |          | X   | X  |
| Events – AEs and SAEs   |          | X   |  |
| Events – SAEs   |          |   | X l   |
| Anti-Cancer Treatment for current malignancy (Post Blinatumomab)  |          |   | X j   |
| Anti- Cancer Radiology for current malignancy (Post Blinatumomab) |          |   | X j   |
| End of Study  |          |   | X  |

- a From 1 year prior to start of Blincyto treatment (see note below)
- b Since Primary disease diagnosis (see note below)
- c From 30 days prior to start of Blincyto treatment (see note below)
- d Chemistry, Haematology and Coagulation assessments relating to Events (AEs/SAEs) should be documented in the CRF from the initiation of Blincyto and up to 30 days after Blincyto treatment completion
- e Concomitant medications to be collected only in the case of SAEs and data entered into concomitant medication form
- f Hospitalization information to be collected only in the case of SAEs and to be entered on SAE form only
- g Closest haematology pre-cycle and closest post cycle haematology assessments to be documented in the CRF
- h Treatment response to be documented in the CRF once pre-cycle and once post-cycle with the closest treatment response data pre and post cycle respectively
- i Response to be recorded in the subsequent anti-cancer therapy or anti-cancer radiology forms
- j For NHL subjects - These assessments will not be documented in the CRF
- k From 7 days prior to start of Blincyto treatment (see note below)
- l From 31 days after completion of treatment through to final chart abstraction, the start of another anti-cancer treatment, HSCT, or after 1 year, whichever is earliest - all SAEs to be reported. After the start of another anti-cancer treatment, HSCT, or after 1 year, whichever is the earliest, through to the end of study/final chart abstraction - only SAEs related to Blincyto and fatal SAEs to be reported.

Note: Medical history diagnosis dates/concomitant medication start dates may pre-date primary diagnosis dates. Furthermore, the diagnosis date of comorbidities may pre-date the disease diagnosis date.

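### RFS counts relapse only in marrow or peripheral blood, so a charted isolated extramedullary relapse is dated late; DFS leaves relapse undefined

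*Protocol*

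**What the plan says.** Section 9.3.2.2 (Efficacy) starts the RFS clock at CR/CRh*/CRi and runs it "until relapse (proportion of blasts in bone marrow > 5% or blasts in peripheral blood after documented" remission, or to death. The parenthesis is a closed list of two criteria. It carries no wording for examples and no reference to the treating physician's diagnosis. By contrast, section 9.3.2.1 takes the specified adverse events as the investigator diagnosed them.

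DFS, for patients who are MRD+ when Blincyto starts, runs "until date of relapse or death". No criteria for relapse are attached.

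Extramedullary disease is not mentioned anywhere in the protocol. Section 9.3.3 lists "active or history of central nervous system (CNS) pathology", but as a co-morbid condition. In Appendix B the on-treatment entry is "Treatment response to be documented in the CRF once pre-cycle and once post-cycle". After treatment, response goes on the forms for later anti-cancer therapy or radiology. No site of relapse is listed.

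RFS is summarised by Kaplan-Meier under section 9.7.2: "Six, 12- and 24-month survival proportions and 95% confidence intervals will also be estimated". On follow-up, section 9.2.1 says "Chart abstractions for each eligible patient will continue for a minimum of 2 years post Blincyto initiation".

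**The concern.** RFS is meant to measure time free of relapse. Suppose leukaemia returns in the CNS or another extramedullary site while marrow and blood are clear. The chart says relapse, but the written rule does not. The RFS time then runs on until marrow blasts exceed 5%, blasts appear in blood, the patient dies, or follow-up ends. A treatment failure is recorded later than it occurred, so the Kaplan-Meier curve and the 6-, 12- and 24-month proportions are pushed upward.

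The undefined relapse in DFS adds a second problem. An abstractor following the chart would count an isolated CNS relapse for DFS in an MRD+ patient. The RFS rule would not count the same kind of event in a responder.

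**Working it through.** **1. Definition check.** Isolated extramedullary relapse with marrow blasts at or below 5% and no blasts in blood:

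| Endpoint | Written event | Counted when it occurs? |
|---|---|---|
| RFS | marrow blasts > 5%, blasts in blood, or death | No; only at a later marrow/blood relapse or death |
| DFS | relapse (no criteria) or death | Depends on the abstractor |
| OS | death | Not affected |

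**2. One hypothetical record.** Remission at month 1, isolated CNS relapse at month 4, marrow relapse at month 10. Written rule: 10 − 1 = 9 months. With the CNS relapse counted: 4 − 1 = 3 months.

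**3. Direction.** Taking an event type out of a time-to-first-event endpoint leaves each patient's time unchanged or longer. The error cannot be downward.

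**4. Size.** The protocol gives no RFS rate, relapse rate or extramedullary share, so there is no stated figure to reproduce and every input is an assumption:

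- RFS exponential with median 7 months: λ = ln 2 / 7 = 0.0990 per month
- relapses are 75% of RFS events
- a share f of relapses is isolated extramedullary (5%, 10%, 20%), with hazard μ = 0.75 f λ
- median lag m of 4 or 8 months from that relapse to a counted event, with hazard κ = ln 2 / m

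True RFS is e^(−λt). Under the written rule,

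S(t) = e^(−λt) + μ (e^(−κt) − e^(−λt)) / (λ − κ).

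At t = 12, e^(−λt) = 0.3048. The multiplier of μ is (0.1250 − 0.3048)/(0.0990 − 0.1733) = 2.42 for m = 4, and (0.3536 − 0.3048)/(0.0990 − 0.0866) = 3.94 for m = 8 (unrounded inputs).

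| f | μ | Excess at 12 months, m = 4 / 8 | 12-month RFS (true 30.5%) | Rise in median (months) |
|---|---|---|---|---|
| 5% | 0.00371 | 0.9 / 1.5 points | 31.4% / 31.9% | 0.2 / 0.3 |
| 10% | 0.00743 | 1.8 / 2.9 points | 32.3% / 33.4% | 0.4 / 0.6 |
| 20% | 0.01485 | 3.6 / 5.9 points | 34.1% / 36.3% | 0.9 / 1.2 |

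**5. Other assumptions.** Take true 12-month RFS as 40% and let 5% of all first events be isolated extramedullary. The written rule then gives 40.8% with a 3-month median lag and 41.5% with a 6-month lag. At 10% of first events it gives 41.7% and 42.9%.

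An outer bound assumes that no counted event ever follows. The excess is then share × (1 − true RFS): 0.05 × 0.60 = 3.0 points and 0.10 × 0.60 = 6.0 points. At a 15% share and true RFS of 30% it is 0.15 × 0.70 = 10.5 points. This bound needs every such patient to avoid marrow relapse, blood relapse and death. It is not an estimate.

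**6. Scale.** Table 3 of the protocol gives 95% half-widths at a 40% proportion of 12.4 points for N = 60 and 7.8 for N = 150. RFS is restricted to responders. The finite-lag figures above lie inside that imprecision, although a larger sample would not remove a bias.

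**The case against.** The strongest reply is that a marrow/blood rule is a legitimate choice of endpoint. It is explicit, reproducible from charts, and matches response criteria that also rest on marrow and blood counts: "Proportion of patients achieving CR (defined as < 5% bone marrow blasts, platelets > 100,000 cells per" microlitre, and so on. No other section contradicts it. Every input to the size is assumed, the larger figures need a high share and a long lag together, and the study tests no hypothesis. An undefined relapse in DFS is the sort of detail an analysis plan may settle. DFS and RFS also have different populations and starting points, and nothing shows that one patient would enter both.

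Most of this stands and limits the point to a minor one. It does not remove it. The RFS rule is fixed in the protocol, not left open, and it dates a charted relapse late in a known direction. If abstractors follow the chart diagnosis instead, the reported RFS departs from its definition, and sites may differ.

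Three stronger readings are tempting but unsupported:

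- **Such a patient stays relapse-free.** Later marrow or blood relapse and death still count, so an event is generally mistimed and is lost only if none of these is observed.
- **RFS is not comparable with the trial and historical data that section 9.9 offers as context.** The protocol does not say how those sources defined relapse. If they used a marrow/blood rule, the change would reduce comparability.
- **CR, CRh\* and CRi should also require absence of extramedullary disease.** Appendix B requires no assessments, so such a criterion would read not examined as absent, and response would depend on how intensively each site looked.

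**Conclusion.** The point holds as a minor one. The written RFS event leaves out isolated extramedullary relapse until a marrow/blood relapse or death follows, and DFS does not say whether it counts. RFS can only be equal or overstated.

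The size is unknown from the protocol. It is about 0.9 to 1.5 points at 12 months if 5% of relapses are isolated extramedullary, and about 6 points only at a 20% share with an 8-month median lag. Both figures rest on the exponential model, the 7-month median and the 75% relapse share. OS, the safety endpoints, the medication-error endpoint and the sample-size tables are unaffected.

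**What to change.** In section 9.3.2.2, give RFS and DFS one relapse definition: marrow blasts > 5%, blasts in peripheral blood, or extramedullary leukaemia documented in the chart, dated at first documentation. Each endpoint keeps its own population and starting date. Report the number of isolated extramedullary relapses, and keep the marrow/blood-only RFS as a sensitivity analysis. Leave the response definitions as they are.

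The cost is slightly less favourable RFS and possibly one relapse-site item. For ALL patients, later anti-cancer treatment and radiology are already abstracted, as are SAEs within the protocol's reporting limits, so many such relapses should leave a dated trace. The timing matters: collection began in Q1 2017 for about 7 years, and Amendment 9 is dated September 2022. A new item would mean returning to existing charts at up to 70 or more sites. Under section 12.1 an amendment also needs ethics approval and, if substantial, submission to PRAC. If that is too much, the wording change and a count from data already collected still remove most of the ambiguity.

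### Remission does not require blast-free blood, yet any later blood blasts count as relapse, so unchanged disease can be scored as response and then as relapse (Protocol 9.3.2.2)

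*Protocol*

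**What the plan says.** All the definitions stand in one list, Protocol Section 9.3.2.2 (Efficacy):

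- CR is "defined as < 5% bone marrow blasts, platelets > 100,000 cells per" µL, with neutrophils above 1,000 per µL.
- CRh* is at most "5% bone marrow blasts, platelets > 50,000 cells per" µL, with neutrophils above 500 per µL.
- CRi is at most "5% bone marrow blasts and incomplete recovery of peripheral blood counts", with no platelet or neutrophil threshold.
- An RFS event is death or relapse, and relapse is "proportion of blasts in bone marrow > 5% or blasts in peripheral blood after documented" CR/CRh*/CRi.
- The RFS clock starts at CR/CRh*/CRi, but the entry closes with "Defined for the subset of subjects who achieved CR".

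On data, Section 9.3.3 collects "Blood count (including Haemoglobin, Platelets, WBC, Neutrophils, Blasts" from 30 days before initiation to 30 days after completion. Appendix B asks for "Closest haematology pre-cycle and closest post cycle haematology assessments to be documented in the CRF" and, as a separate item, "Treatment response to be documented in the CRF once pre-cycle and once post-cycle".

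**The concern.** The remission and relapse rules treat the same finding differently. Circulating blasts do not prevent a remission from being recorded, but once it is recorded they are enough for a relapse, at any level and without confirmation. Someone whose marrow clears to 5% or below while blasts persist in the blood meets a remission definition. The next blood count, showing the same blasts, then meets the relapse definition.

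Two results could be affected. The response proportion could include patients who still have circulating leukaemia. RFS could include very short times that record no real loss of response. The responder set also supplies the denominator for the MRD proportion and, for patients in CR, the base for the transplant proportion and post-transplant mortality. Response in the late first-relapse subgroup matters most: Section 9.5 says CHMP asked for this subgroup so that its benefit-risk could be evaluated.

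**Working it through.** **1. The criteria side by side (Protocol 9.3.2.2).**

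| State | Marrow blasts | Blood counts | Blasts in blood |
|---|---|---|---|
| CR | < 5% | platelets > 100,000, neutrophils > 1,000 | not mentioned |
| CRh* | ≤ 5% | platelets > 50,000, neutrophils > 500 | not mentioned |
| CRi | ≤ 5% | incomplete recovery, no thresholds | not mentioned |
| Relapse | > 5% | none | any, after documented remission |

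In the marrow column no value satisfies both a remission and the relapse criterion. In the last column the rules do not separate. No other part of the protocol adds a blood-blast condition to remission.

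**2. Can the data trigger the conflict?** Yes. Blood-count blasts are collected, and both haematology and response are taken at the nearest point before and after each cycle. A post-cycle remission can therefore be followed by a count before the next cycle that shows blasts. Appendix B lists haematology only up to 30 days after completion, so this route is confined to that window.

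**3. The plan's own figure.** Section 9.5 gives 67.6% to 92.4% for an observed 80% in 40 patients. Check: 1.96 × √(0.80 × 0.20 / 40) = 0.124, and 80% ± 12.4 points gives 67.6% to 92.4%. It reproduces, as do all 24 cells of Table 3 within rounding. There is no arithmetic error, and this point changes no printed figure.

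**4. Effect per patient, with no assumed frequency.**

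- Response, N = 200: 100/200 = 0.5 point.
- Response, 40 late first-relapse patients: 100/40 = 2.5 points.
- RFS, if 80% of those 40 respond (32 patients) and all enter RFS: 100/32 = 3.1 points on the early curve.

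**5. Range over an assumed share f of responders with circulating blasts.** The protocol gives no value for f, so 0% to 15% is purely illustrative. Corrected response = p × (1 − f). Early RFS under the present text is about 1 − f if all responders enter RFS. The 80% is the example in Section 9.5; the 50% at N = 200 is an assumption.

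| f | Response, n = 40, p = 80% | 95% CI | Early events among 32 | Response, N = 200, p = 50% | Early RFS |
|---|---|---|---|---|---|
| 0% | 80.0% | 67.6 to 92.4 | 0 | 50.0% | 100% |
| 2% | 78.4% | 65.6 to 91.2 | 0.6 | 49.0% | 98% |
| 5% | 76.0% | 62.8 to 89.2 | 1.6 | 47.5% | 95% |
| 10% | 72.0% | 58.1 to 85.9 | 3.2 | 45.0% | 90% |
| 15% | 68.0% | 53.5 to 82.5 | 4.8 | 42.5% | 85% |

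For scale, the Table 3 half-width is 12.4 points at n = 40 and 80%, and 6.9 points at N = 200 and 50%. The shifts reach 12.0 and 7.5 points only at f = 15%.

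**6. Which patients enter RFS.** If the closing sentence of the RFS entry means strict CR, CRh* and CRi patients are outside RFS. Only patients with platelets above 100,000, neutrophils above 1,000 and circulating blasts could then cause a spurious early event. If it means the composite, CRh* and CRi patients enter too. The composite response proportion is exposed under either reading.

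**The case against.** A reader might infer that a patient can be in remission and relapsed on the same date. The text does not support that. Relapse must come after a documented remission, so the rule is sequential. It leaves open whether blasts that merely persist count at the next assessment, and nothing excludes them. The fine detail of timing could properly sit in an analysis plan that is not shown. The two definitions, however, are fixed in the protocol and disagree there.

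A reader might also infer that response and RFS are in fact mis-scored. That is not shown. No frequency is given, and zero is compatible with the text. Full count recovery together with circulating blasts is a narrow combination, so the effect on strict CR may be close to nil.

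Treatment response is also its own charted item in Appendix B, taken from local records. The treating physician may already have withheld a remission from a patient with circulating blasts. This stands as a reason why the practical effect could be small. It does not resolve the conflict: 9.3.2.2 sets numeric criteria for efficacy and does not say that the charted response overrides them. The reliance on investigator diagnosis in 9.3.2.1 is attached to the adverse events.

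Finally, these are secondary, descriptive endpoints without a hypothesis test, and the protocol is at Amendment 9 with interim reports already issued. Both facts limit the weight of the point and add to the cost of the change.

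**Conclusion.** The inconsistency is real and lies in the wording of 9.3.2.2. Followed as written, the rules can score a patient with unchanged disease as a responder and then as relapsed. That can overstate the response proportion, with CRi most exposed because it has no count thresholds, and can shorten RFS. How far RFS is affected turns on the meaning of the CR subset.

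The total size cannot be derived from the protocol. What can be stated is 0.5 point of response per affected patient at N = 200 and 2.5 points in 40 late first-relapse patients; the scenario table rests on assumed shares. The primary safety objectives, the study size and Tables 2 and 3 are unaffected. The correction is worth making because the late first-relapse response result is small-sample and is meant to inform benefit-risk.

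**What to change.** In Section 9.3.2.2:

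1. Add to CR, CRh* and CRi the condition that peripheral blood is free of blasts, judged on the blood-count blast result closest to the response assessment.
2. Keep the relapse criterion, but state that a relapse event requires an assessment later than the one that documented remission. This alone would not be enough, because persisting blasts would still count at the later assessment.
3. Where no peripheral blast result is charted, classify on marrow and counts as now, and report how many patients this affects.
4. State whether the RFS subset is strict CR or CR/CRh*/CRi, since the effect on RFS depends on it.

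The cost is a phrase in three definitions and a short derivation rule; no new data item is needed. There are three downsides. The response proportion may fall slightly. Some blast results will be missing or not aligned with the marrow date, and the inconsistency remains for patients with no result. The definition will also differ from that in earlier interim reports, which can be handled by reporting response under the previous definition as well.
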